13.2.1.2 Reporting Results

13.2.1.2.1 Summary of Descriptive Statistics

For each responder analysis and treatment group, the number and proportions (expressed as percentages) of responders at each scheduled time point will be calculated. These proportions, along with 95% CIs, will be summarized by scheduled time point. In addition, the differences in proportions between a tildacerfont and placebo subjects and their 95% CIs will be presented. If less than 5 responders are in a treatment group, exact (Clopper-Pearson) CIs will be used.

13.2.1.2.2 Summary of Analysis Results

The parameter estimates (i.e., odds ratios, the 95% CI of odds ratios, nominal p-values) from the logistic model will be reported by scheduled time point (i.e., Week 4, Week 8, and Week 12) in reverse time order.

13.2.1.2.3 Graph Presentation

The proportion of responders from the model-based analyses will be displayed graphically by treatment group over time with the y-axis representing the proportion meeting the responder definition and the x-axis the visits Week 4, Week 8, and Week 12.

A cumulative distribution plot of responders will be plotted against baseline DHEAS. This figure will be produced by treatment group and overall.

13.2.1.3 Supportive Analyses

The analysis of the secondary endpoint will be repeated using the additional thresholds of 25% and 20% reduction from baseline in DHEAS.

13.2.1.4 Subgroups

The primary endpoint will be descriptively summarized for each subgroup specified in [Section 10.8](#) for the mITT Analysis Set.

13.3 Exploratory Efficacy Analyses

The analysis population for the exploratory efficacy analyses is the mITT analysis set ([Section 8.2](#)).

The exploratory endpoints explore clinical outcomes: ACTH ([Endpoint 3.1](#)), DHEA ([Endpoint 3.2](#)), T ([Endpoint 3.3](#)), A4 ([Endpoint 3.4](#)), 17-OHP ([Endpoint 3.5](#)), 11OHA4 ([Endpoint 3.6](#)), 11OHT ([Endpoint 3.7](#)), 11KA4 ([Endpoint 3.8](#)), 11KT ([Endpoint 3.9](#)).

These biomarkers will be descriptively summarized; no statistical analyses will be performed.

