
Statistical Methods:
 
Statistical Hypotheses
 
Efficacy endpoints will be evaluated using the following hypothesis-testing schema: Each tildacerfont dose will be compared with placebo. The null hypothesis will be that there is no difference in the endpoint between a given dose level of tildacerfont and placebo. The alternative hypothesis will be that there is a difference.
 
Sample Size
 
A sample size of 33 subjects with 2:1 randomization will provide at least 80% power to detect a difference of 164 mcg/dL in mean DHEAS between at least one dose of tildacerfont and placebo assuming a standard deviation of 154 mcg/dL and a two-sided alpha of 0.05. Accounting for a 15% drop out, the final sample size is N=39 (n=26 for tildacerfont group and n=13 for placebo). Subjects will be randomized using the strata of Screening DHEAS ($\leq 1.2 \times$ ULN, $> 1.2 \times$ ULN).
 
Analysis Populations
 
 The Intent-to-Treat (ITT) Population will include all subjects randomized in the study. The modified Intent-to-Treat (mITT) Population will include subjects in the ITT Population who have at least one dose of study drug, a baseline DHEAS assessment and at least one post baseline DHEAS assessment. The Safety Population will include all subjects who receive at least 1 dose of study drug in the study.

- The PK Population will include all randomized subjects who receive at least 1 dose of tildacerfont and have at least 1 evaluable PK sample.

Efficacy Analyses

All efficacy analyses will be conducted on mITT Population using a 2-sided alpha of 0.05. No adjustment for multiplicity is planned as this study is exploratory in nature.

The primary endpoint, the change from baseline in DHEAS, will be used to evaluate the preliminary efficacy of tildacerfont therapy relative to placebo and will be summarized using an analysis of covariance model (ANCOVA) with baseline DHEAS as a covariate and randomization strata and dose level as independent variables. Additional covariates may be added in the statistical analysis plan. The proportion of subjects meeting specific DHEAS thresholds will be summarized using exact tests through logistic regression using the randomization strata and dose level.

Exploratory hormone/androgen change endpoints will be analyzed using a similar methodology as the primary endpoint.

Safety Analyses

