8.3.4. Efficacy Analyses

All efficacy analyses will be conducted on mITT Population using a 2-sided alpha of 0.05. No adjustment for multiplicity is planned.

The primary endpoint, the change from baseline in DHEAS, will be used to evaluate the preliminary efficacy of tildacerfont therapy relative to placebo and will be summarized using an analysis of covariance (ANCOVA) model with baseline DHEAS as a covariate and randomization strata and dose level as independent variables. Each Treatment Period's final DHEAS assessment (ie, Week 4, Week 8, and Week 12) is the dependent variable. Additional covariates may be added in the SAP.

The proportion of subjects meeting specific DHEAS thresholds will be summarized using exact tests through logistic regression using a similar variable structure as the primary endpoint:

- DHEAS \geq 30% reduction from baseline vs <30% reduction from baseline
- DHEAS \leq ULN vs >ULN.

Additional covariates may be added in the SAP. Missing values for proportion endpoints will not be imputed and will be assumed to be failures.

Exploratory hormone and androgen endpoints will be summarized using an ANCOVA model using a similar variable structure as the primary endpoint. Additional endpoints may be specified in the SAP.

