9.1 Presentation of Summary Statistics

For most summary statistics, data will be analyzed and displayed in tabular format.

Unless otherwise specified, continuous efficacy hormones ([Section 5.2.2.1](#)) will be summarized using a 11-point descriptive statistics (i.e., n, mean, standard deviation [SD], median, 25% quartile [Q1], 75% quartile [Q3], minimum, maximum, geometric mean, geometric coefficient of variance [CV%], 95% confidence interval [CI] for geometric mean [including geometric mean ratio and its 95% CI]).

All other continuous variables will be summarized using an 8-point descriptive summary (n, mean, SD, median, Q1, Q3, minimum, and maximum) unless otherwise specified.

The same number of decimal places as in the observed value will be presented when reporting minimum and maximum; 1 additional decimal place than in the observed value will be presented when reporting mean, median, Q1, Q3, geometric mean, 95% CI; 2 additional decimal places than in the observed value will be presented when reporting SD. Geometric CV% will be reported to one decimal place.

All categorical/qualitative data will be presented using the frequency of events and percentages. All percentages will be presented to 1 decimal place, unless otherwise specified. Percentages equal to 100 will be presented as 100% and percentages will not be presented for zero frequencies, with the exception of binary variables. For summaries of AEs and concomitant medications (CMs), the percentages will be based on the number of subjects who received study drug.

All analyses and summaries will be produced using SAS® version 9.4.

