9.3.13 Geometric Mean Ratio and Percent Change

For efficacy hormone variables ([Section 5.2.2.1](#)), the geometric mean ratio (GMR) and percent change from baseline will be calculated by treatment group and dose level. The GMR is derived from the natural logarithm of the post-baseline value divided by the baseline value [$\log(\text{post-baseline}/\text{baseline})$]. The GMR is the exponential function of the mean of $\log(\text{post-baseline}/\text{baseline})$. The 95% CI of GMR is the exponential function of the 95% CI of the mean [$\log(\text{post-baseline}/\text{baseline})$]. The percent change is derived as $100 \times (\text{GMR} - 1)$. The 95% CI of percent change is $100 \times (95\% \text{ CI of GMR} - 1)$.

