13.1.3 Statistical Modeling and Testing

13.1.3.1 Analysis of Covariance

The normality of residuals will be evaluated (Section 10.2). If the distribution of residuals is judged non-normal, then the analysis will be repeated using rank values in place of the original values. Statistical testing for the exploratory efficacy endpoint will be performed using a (rank-based, if non-normal residuals) ANCOVA model. The model will comprise the (rank of, if non-normal residuals) log-transformed change from baseline value as the dependent variable; randomized treatment group (0 = placebo, 1 = tildacerfont) as a fixed effect; and the log-transformed baseline serum DHEAS and age as a continuous covariates. The estimation method for the ANCOVA model will be maximum likelihood.

The ranked value is obtained by ranking all non-missing ratio of post-baseline/baseline values, if a rank-based model is used. The formal testing for the group difference ($\neq 0$) between tildacerfont and placebo treatment groups in change from baseline will be conducted at the scheduled time point of Week 12 visit using the aforementioned ANCOVA model. Statistically significant difference will be declared if two-sided p-value < 0.05 .

The statistical model used to characterize the primary endpoint at Week 12 will also be used to characterize the tildacerfont response at earlier weeks, replacing the Week 12 outcome with the Week 8 and the Week 4 outcomes.

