13.3.1 Reporting Results

Descriptive statistics (11-point) for the exploratory biomarker assessments, change from baseline, and % change from baseline will be presented by treatment group and scheduled time point (i.e., Baseline, Week 4, Week 8, and Week 12).

For each treatment group, a spaghetti plot of select hormone levels and change from baseline over time (Baseline, Week 4, Week 8, and Week 12) will be plotted with the means at each time point overlaid. The select hormones are ACTH, 17-OHP, and A4.

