15 CHANGES RELATIVE TO THE PROTOCOL-SPECIFIED ANALYSIS

The study intended to enroll up to 40 subjects but was discontinued early on the basis of a business decision made by the sponsor. Due to the resulting small sample size, the exploratory efficacy analyses described in Protocol [Section 8.3.4](#) are replaced with summaries of descriptive statistics.

The MMRM analysis introduced in [Section 13.1](#) of this SAP is not mentioned in the protocol. However, to avoid protocol amendment, inclusion of this analysis in the SAP – well in advance of the database lock – is meant to serve the same intent.

The secondary endpoint of 30% reduction from baseline in DHEAS is mentioned in the protocol and sections [6](#), [6.1.2](#), [9.3.12](#) and [13.2](#) of this SAP. However, since some subjects have entered the study up to 25% lower than anticipated DHEAS into the study, it is necessary to assess respond at lower threshold of reduction at 25% and 20% in addition to originally planned 30% reduction.

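### SAP 13.3 pre-specifies no tildacerfont/placebo estimate for the nine exploratory hormones; the only intervals for change are within-arm

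*SAP*

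**What the plan says.** The exploratory objective in both documents is the effect of tildacerfont on ACTH, DHEA, T, A4, 17-OHP, 11OHA4, 11OHT, 11KA4 and 11KT. The protocol's synopsis sets a general scheme for efficacy endpoints: "Each tildacerfont dose will be compared with placebo". Protocol 8.3.4 applies it to these hormones: "Exploratory hormone and androgen endpoints will be summarized using an ANCOVA model using a similar variable structure as the primary endpoint".

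SAP 13.3 withdraws that model: "These biomarkers will be descriptively summarized; no statistical analyses will be performed". SAP 13.3.1 states what is produced instead: "Descriptive statistics (11-point) for the exploratory biomarker assessments, change from baseline, and % change from baseline will be presented by treatment group" and visit, with spaghetti plots by arm for ACTH, 17-OHP and A4. Under SAP 9.1 the 11 points are n, mean, SD, median, quartiles, minimum, maximum, geometric mean, geometric CV% and a 95% CI "for geometric mean [including geometric mean ratio and its 95% CI". SAP 9.3.13 defines that ratio as post-baseline over baseline, and "the geometric mean ratio (GMR) and percent change from baseline will be calculated by treatment group and dose level".

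SAP 15 discloses the departure. It says the study was stopped early for business reasons, and continues: "Due to the resulting small sample size, the exploratory efficacy analyses described in Protocol" Section 8.3.4 give way to descriptive summaries.

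One sentence points the other way. In SAP 13.1.3.1, under the primary analysis: "Statistical testing for the exploratory efficacy endpoint will be performed using a" (rank-based if needed) ANCOVA.

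**The concern.** A GMR interval computed inside one arm answers a before-after question. If a hormone moves in both arms for a reason other than the drug, the tildacerfont interval absorbs that movement. Setting the two arms' intervals side by side does not fully repair this. With 2:1 allocation the active arm is twice the size of placebo, so its interval excludes 1 more easily when the true change is identical. The table could then show a reduction on tildacerfont and none on placebo.

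Protocol 1.1.3 rests the rationale on lowering adrenal androgens by reducing ACTH, so these hormones bear on mechanism. Protocol 1.2.1 justifies the placebo arm as the way to attribute DHEAS change to treatment and to allow for inherent variability. It says this of DHEAS, but the reasoning carries over. SAP 4 allows the planned outputs to go into regulatory submissions or manuscripts.

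**Working it through.** **1. What remains for the exploratory hormones.** Of the 11 points, only the geometric mean and the GMR carry intervals, and both are computed within an arm. No tildacerfont/placebo ratio, difference or interval appears in SAP 9.1, 9.3.13, 13.3 or 13.3.1.

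**2. Does the stated reason fit?** SAP 15 gives small sample size. At that same sample size the SAP keeps an ANCOVA for DHEAS (13.1.3.1), adds an MMRM (13.1.3.2), and repeats both in subjects who do and do not meet inclusion criterion 3 (13.1.5); each of those groups is a subset of the sample. SAP 10.1 also keeps the randomisation stratum for efficacy models whose outcome is not derived from DHEAS. The nine exploratory hormones are the only such efficacy endpoints, so under 13.3 that rule has nothing to act on.

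**3. The plan's own figure.** Protocol 8.1 and SAP 7 give a difference of 164, SD of 154, two-sided alpha of 0.05, 80% power and 2:1 allocation. Placebo n = 1.5 × (1.960 + 0.842)² × (154/164)² = 10.4, so 11, with 22 on tildacerfont: 33. Then 33/0.85 = 38.8, so 39. Both figures reproduce (power 82.2% by the normal formula, 79.8% by t). They concern DHEAS and serve here only to fix 22/11 as the planned evaluable size.

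**4. Illustration of the risk.** These assumptions are not in the documents: log-change SD s of 0.3 to 0.5; an equal true fall of 10 to 20% in both arms; no drug effect; sizes 22/11 (planned), 14/7 and 10/5 (illustrative, as the number actually enrolled is not given).

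For an arm of size n with true log change δ, the 95% CI of the GMR lies wholly below 1 with probability P(T < −t(0.975, n−1)), where T is noncentral t with n−1 degrees of freedom and noncentrality δ√n/s. The arms are independent, so the chance that tildacerfont lies below 1 and placebo does not is p_T × (1 − p_P).

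Example: 22/11, s = 0.4, 15% fall, δ = ln 0.85 = −0.1625.
- Tildacerfont: noncentrality −1.906, critical t 2.080, p_T = 44.4%.
- Placebo: noncentrality −1.348, critical t 2.228, p_P = 23.0%.
- Discordant reading: 0.444 × 0.770 = 34.2%. Simulating 40,000 trials of this case gave 34.1%.

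Chance of the discordant reading for falls of 10 / 15 / 20%:

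| SD | 22/11 | 14/7 | 10/5 |
|---|---|---|---|
| 0.3 | 29 / 43 / 36% | 20 / 36 / 45% | 15 / 28 / 42% |
| 0.4 | 19 / 34 / 43% | 14 / 25 / 37% | 11 / 19 / 29% |
| 0.5 | 14 / 26 / 38% | 10 / 18 / 28% | 8 / 14 / 21% |

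The overall range is 8 to 45%. With no shared change it is 0.025 × 0.975 = 2.4%.

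**5. The between-arm interval.** A shared change cancels in tildacerfont/placebo, so with no drug effect its 95% CI lies wholly below 1 in 2.5% of trials whatever the drift. Before any gain from baseline adjustment, its width is the estimate times or divided by exp[t(0.975, N−2) × s × √(1/n_T + 1/n_P)]. For 22/11 and s = 0.3 this is exp(2.040 × 0.3 × 0.369) = 1.25. Across s of 0.3 to 0.5 the factor is 1.25 to 1.46 at 22/11, 1.34 to 1.62 at 14/7 and 1.43 to 1.81 at 10/5.

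**The case against.** The strongest reply is that this is a disclosed choice about exploratory endpoints. SAP 15 states the change and the reason, and SAP 4 says the methods were fixed before freeze and unblinding. DHEAS is the primary, powered endpoint, so putting it ahead of 27 exploratory contrasts is ordinary triage. Small-sample estimates would also be vague: at 14/7 with SD 0.4, an observed 30% reduction would carry an interval of about 0.48 to 1.03. All of this stands, and it limits the weight of the point. It supports omitting tests. It does not show why within-arm intervals should survive and the between-arm interval should not.

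Several stronger readings are tempting and not supported:

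- **That there is no comparator, or that a shared drift would be hidden.** Placebo is summarised at the same visits and plotted for three of the hormones, so drift would be visible. From each arm's n, GMR and CI a reader could even derive an unadjusted between-arm ratio. What is missing is a pre-specified, baseline-adjusted one.
- **That the SAP will treat a within-arm interval excluding 1 as a drug effect.** No section says so. The risk lies in how the table may be read.
- **That the within-arm rate alone measures the problem.** Under the assumptions above, the tildacerfont interval alone lies below 1 in 9 to 91% of trials. That ignores the placebo column, and the top value pairs the largest assumed drift and smallest SD with a sample size overtaken by early stopping.
- **That SAP 13.1.3.1 still plans ANCOVA tests of these hormones.** The sentence sits in the primary section and its model uses baseline DHEAS, so it is probably a wording slip.

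**Conclusion.** The point holds as a modest, inexpensive improvement to an exploratory analysis. The objective is an effect of tildacerfont, the protocol planned a comparison with placebo, and the SAP leaves no pre-specified between-arm estimate for any of the nine hormones. The sample-size reason covers p-values but not the contrast.

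The text-based part rests on no assumption. The 8 to 45% does: the documents give neither the number enrolled, nor the SD of any of these hormones, nor any evidence of a shared fall. If there is no shared change, the excess risk disappears. The figures show that the misreading is possible at realistic sizes, not that it will occur. The primary and secondary DHEAS analyses do compare the randomised arms and are unaffected.

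**What to change.** In SAP 13.3 and 13.3.1, report for each hormone at Weeks 12, 8 and 4 the tildacerfont/placebo ratio of post-baseline/baseline geometric means with its 95% CI. Take it from a log-scale ANCOVA with treatment, log baseline of that hormone and, following SAP 10.1, the randomisation stratum. Label it exploratory and give no p-values.

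SAP 13.1.3.1 moves to ranks when residuals are non-normal, which would yield no ratio, so a fallback is needed. If residuals are clearly non-normal, report the between-arm difference in medians with the bootstrap interval already defined in SAP 13.1.4.2, noting that it is not baseline-adjusted.

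Add a sentence that within-arm GMR intervals are descriptive and are not evidence of a treatment effect. Amend SAP 15 to match. As an editorial matter, correct the word exploratory in the SAP 13.1.3.1 sentence.

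The cost is wording and reuse of the DHEAS code, with no new data or subjects. The drawback is 9 × 3 = 27 further unadjusted intervals, wide at these sizes; the multiplicity caution in SAP 10.6 should be extended to name them.

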13.3.1 Reporting Results

Descriptive statistics (11-point) for the exploratory biomarker assessments, change from baseline, and % change from baseline will be presented by treatment group and scheduled time point (i.e., Baseline, Week 4, Week 8, and Week 12).

For each treatment group, a spaghetti plot of select hormone levels and change from baseline over time (Baseline, Week 4, Week 8, and Week 12) will be plotted with the means at each time point overlaid. The select hormones are ACTH, 17-OHP, and A4.

14 SAFETY ANALYSES

Safety will be assessed by AEs, SAEs, AEs leading to discontinuation/withdrawal, DLTs, AESIs, physical examination, vital signs, ECGs, clinical laboratory tests, and psychiatric evaluations for suicide risk by C-SSRS. All analyses of the safety data will be performed using

the safety analysis set, based on the actual treatment a subject received. All descriptive statistics (described in Section 9.1) will be presented by treatment group (including dose level).

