5 STUDY DESIGN

This is a multi-center, randomized, placebo-controlled, dose escalation clinical study that will evaluate the preliminary safety and efficacy of up to 12 weeks of double-blinded treatment with tildacerfont (50 mg, 100 mg, and 200 mg once daily [QD]) in adult women subjects with PCOS who have elevated adrenal androgens at baseline. Up to approximately 40 adult subjects will be randomized into the study.

Subjects who meet all eligibility criteria at Screening will be randomized into the Treatment Period in a 2:1 ratio to receive either tildacerfont or matching placebo. Subjects randomized to the tildacerfont group will receive 3 escalating dose levels of tildacerfont with each dose level administered for 4 weeks. Subjects randomized to placebo will remain on placebo over the full 12-week Treatment Period. Upon completion of the Treatment Period, subjects will return to the clinic within 30 days following their last dose for a Follow-up visit.

Clinical visits during the Treatment Period and Follow-up Period will include safety, efficacy, and PK assessments. [Figure 1](#) depicts study visits from Screening Period to Follow-up Period.

The maximum duration of Study SPR001-210 per subject is expected to be up to 204 days (i.e., up to 30 days of optional DHEAS screening, a maximum of 30-day Screening Period, a 12-week Treatment Period, and a 30-day safety Follow-up Period). Subjects randomized to tildacerfont will receive up to 12 weeks of treatment with tildacerfont. Assessments and procedures for evaluation of safety, efficacy, and PK will be conducted per the protocol-specified schedule (see Appendix A: [Table 6](#) and [Table 7](#)).

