9.3.16 Adverse Events

AEs are those AEs with onset date from the signing of the ICF until the end of the follow up period.

Treatment-emergent adverse events (TEAEs) are defined as any AEs, regardless of relationship to study drug, that have an onset or worsening in severity on or after the first dose of study drug until 30 days after the final dose of study drug (Follow-up visit). For AEs that occur on the date of the first dose of study drug, the time of onset (before or after intake of study drug) will be specified and used for comparison.

If a subject discontinues study drug but remains in the study, AEs with onset date after 30 days of last dose of study drug until the end of the follow up period will be considered post-treatment adverse events.

Related TEAEs are those reported by investigators as possibly related, probably related, or definitely related to the study drug.

AESIs are events that do not meet SAE criteria but must be monitored on an ongoing basis as defined in Protocol [Section 7.2.8](#) and identified in the AE eCRF page.

Serious AEs (SAEs) are defined in Protocol [Section 7.2.6](#) and identified in the AE eCRF page.

Dose-limiting toxicities are defined as a Common Terminology Criteria for Adverse Events (CTCAE) Grade 3 or higher TEAE that is also considered at least possibly related to study drug.

Suspected unexpected serious adverse reactions (SUSARs) is an AE that is serious, related to study drug, and is not expected in the targeted disease (PCOS).

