9.3.17.1 Record-Level Actual Treatment and Dose for an Adverse Event

TEAEs are those AEs with onset date from the date of first dose of randomized study drug until the end of the study (Follow-up). The treatment will be the randomized study treatment (tildacerfont or placebo) and the dose level (50 mg QD, 100 mg QD, 200 mg QD) will be the actual tildacerfont dose received on the onset date of the TEAE records.

Post-treatment AEs (within 30 days after study drug discontinuation) will be assigned the last treatment and dose level that the subject was on before study drug discontinuation. Post treatment AEs after 30 days post study drug discontinuation will be assigned to no treatment.

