14.1 Adverse Events

All AE verbatim terms reported on the eCRFs will be coded using the Medical Dictionary for Regulatory Activities (MedDRA® version 24.1).

All reported AEs (including non-TEAEs) will be listed. Separate listings will be provided for SAEs, TEAEs leading to study drug discontinuation, DLTs, AESIs, SUSARS, AEs related to adrenal insufficiency, and AEs related to COVID-19.

For all TEAE tables, counting will be by subject and not by event. Additionally, if a subject reported the same TEAE on multiple occasions, the highest severity (severe > moderate > mild) or study drug relationship (related > probable > possible > unlikely > unrelated) recorded for the event will be summarized. All TEAE summary tables will present the number and percentages of subjects reporting TEAEs, unless otherwise specified. A summary of TEAEs by severity, seriousness, and relation to study drug will be tabulated.

An overall summary of TEAEs will be presented. The overall summary will include the number and percentage of subjects experiencing any AEs, TEAEs, study drug related TEAEs, TEAEs by maximum severity (highest toxicity grade), SAEs, study drug related SAEs, DLTs, SUSARs, TEAEs of adrenal insufficiency, TEAEs leading to study drug discontinuation, and deaths.

The number and percentage of subjects experiencing each TEAE, study drug related TEAE, and SAEs will be summarized by treatment group according to system organ class and preferred term. An additional table including only preferred term summarized by treatment for the number and percentage of subjects experiencing each TEAE will be presented as well.

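### On the natural reading of the SAP, dose-level adverse-event percentages cover 28 to 58 days per completer against about 114 days for placebo, which lowers them relative to placebo in expectation

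*SAP*

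**What the plan says.** SAP 14 applies one general rule to all safety data: descriptive statistics "will be presented by treatment group (including dose level". The protocol synopsis likewise plans safety summaries by treatment group and dose level. SAP 14.1 is less specific. It says of TEAEs that "counting will be by subject and not by event", and that the main tables "will be summarized by treatment group according to system organ class and preferred term".

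SAP 9.3.17.1 sets the attribution rule. The dose level of a TEAE "will be the actual tildacerfont dose received on the onset date of the TEAE records". Events within 30 days after discontinuation "will be assigned the last treatment and dose level that the subject was on before study drug discontinuation". The dose levels named there are 50, 100 and 200 mg; no period is defined for a placebo event.

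TEAEs are collected "on or after the first dose of study drug until 30 days after the final dose of study drug" (SAP 9.3.16). Tildacerfont is escalated "with each dose level administered for 4 weeks" (SAP 5), while placebo runs for the full 12 weeks (SAP 5.2.1). For adverse events, "the percentages will be based on the number of subjects who received study drug" (SAP 9.1). Neither document plans a rate per unit of exposure.

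**The concern.** The percentage of subjects with at least one event rises with the length of observation. Tildacerfont follow-up is cut into three pieces by dose. If placebo follow-up is not cut in the same way, each dose column is compared with a placebo column that has had two to four times as long to collect events. The drug would then tend to look better tolerated than placebo at each dose with no true difference. The 200 mg column also takes the follow-up month, so an apparent step up from 100 to 200 mg could come from the attribution rule alone.

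Safety is a stated objective, and SAP 4 allows these analyses to be used in regulatory submissions and manuscripts. The study also stopped early (SAP 15), so raw percentages from a small sample will carry much of the safety reading.

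**Working it through.** The plan states no adverse-event rate, so there is no safety figure of its own to reproduce. The event rates below are assumptions, shown over a range. The planned group sizes, 26 and 13, come from Protocol 8.1 and SAP 7.

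**Observation windows for a completer**
- 50 mg: 28 days
- 100 mg: 28 days
- 200 mg: 28 + 30 = 58 days
- Placebo, undivided: 84 + 30 = 114 days

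The tildacerfont windows sum to 28 + 28 + 58 = 114 days, so a pooled tildacerfont column matches placebo. For a subject who stops early, the 30-day tail goes to the dose at which she stopped.

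**Expected percentages with no true difference**

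Assume the same constant hazard h in both arms. With 12-week incidence p, h = −ln(1 − p)/84, and the chance of at least one event in d days is 1 − exp(−h·d) = 1 − (1 − p)^(d/84).

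For p = 40%:
- 28 days: 1 − 0.6^(28/84) = 15.7%
- 58 days: 1 − 0.6^(58/84) = 29.7%
- 114 days: 1 − 0.6^(114/84) = 50.0%

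| Assumed 12-week incidence | 50 mg | 100 mg | 200 mg | Placebo |
|---|---|---|---|---|
| 20% | 7% | 7% | 14% | 26% |
| 40% | 16% | 16% | 30% | 50% |

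To equal the placebo column, the true hazard would have to be 114/28 = 4.1 times placebo at 50 or 100 mg, and 114/58 = 2.0 times at 200 mg.

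**Sensitivity to the assumptions**
- Follow-up events ignored (28 against 84 days) and a placebo rate of 50% over those 84 days: 1 − 0.5^(28/84) = 20.6% in each dose column.
- Hazard three times higher in the first 28 days and a whole-study placebo rate of 50%: 29.0%, 10.8% and 21.1%. The pattern across doses changes, but each stays below placebo.

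**How often all three doses would look lower**

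Simulation with 26 tildacerfont and 13 placebo subjects, equal hazards, and windows treated as independent:

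| Assumed whole-study placebo rate | All three doses below undivided placebo | All three below period-matched placebo |
|---|---|---|
| 30% | 76% | 7% |
| 50% | 86% | 8% |
| 70% | 92% | 9% |

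At 22 and 11 subjects the middle column becomes 72%, 83% and 89%.

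**The case against.** The strongest objection is that the SAP never states that the placebo adverse-event column spans the whole study. The table in SAP 9.3.17 lists planned treatment by period for placebo as well as tildacerfont, so the data structure would support a split. Table layouts are in separate mock shells (SAP 9) that are not among the documents. This stands as a limit: the undivided column is an inference. It remains the natural reading, because the rule written specifically for adverse events (SAP 9.3.17.1) does not divide placebo, and SAP 9.3.14.1 counts placebo as one constant level, though only for compliance.

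SAP 14.1 and Protocol 8.3.5 also specify adverse-event summaries by treatment group alone. A pooled comparison built that way is sound. That does not remove the dose-level display that SAP 14 and the protocol synopsis call for.

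Three stronger readings are tempting, and the documents do not support them:
- **That every dose will look safer than placebo.** This holds in expectation. It is not certain at the planned size, and is less so at the smaller actual size, which the SAP does not give.
- **That these columns are the only dose-specific safety display.** Laboratory, vital-sign and ECG data are summarized by scheduled time point (SAP 14.2 to 14.4). Weeks 4, 8 and 12 correspond to the three doses, so those comparisons are already matched in time.
- **That the percentage base is everyone treated, even in the higher-dose columns.** SAP 9.1 does not say whether it means any study drug or that dose level. SAP 12.1 counts a subject in each dose level received, but only for exposure summaries. The window bias does not depend on this.

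Finally, the study is exploratory, no safety test is planned, events are listed individually, and exposure duration is summarized by dose level. A careful reader could therefore see that exposure differs. This limits the harm, but does not make the percentages comparable.

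**Conclusion.** The point holds for dose-level adverse-event incidence. Following the written attribution and counting rules, with placebo undivided, biases each dose column downward relative to placebo in expectation: about 16, 16 and 30% against 50%, or 7, 7 and 14% against 26%, at assumed 12-week incidences of 40% and 20%. The follow-up month roughly doubles the 200 mg figure relative to 50 and 100 mg.

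The exact sizes rest on completers, a constant and equal hazard, and assumed event rates. The direction needs only the unequal windows and the undivided placebo column. Pooled tildacerfont versus placebo comparisons and the time-point summaries are outside the problem. If the mock shells already split placebo by period, what remains is that the SAP should say so.

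**What to change.** In SAP 9.3.17.1, 14 and 14.1:
- Assign placebo events to the matching periods: Day 1 to Week 4, Week 4 to Week 8, and Week 8 to 30 days after the last dose.
- State that the denominator of each dose or period column is the subjects who entered that period.
- Add exposure-adjusted rates. Period-matched placebo corrects each dose-versus-placebo pair, but the 58-day column still cannot be compared directly with the 28-day columns.
- Present pooled tildacerfont versus placebo as the main adverse-event comparison.

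The cost is SAP and table-shell wording and some extra tabulation of data already collected. The downside is a few more table columns with small counts.
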